9.2.2 Run-In Phase

Subjects in groups 2, 3, and 4 will undergo a run-in phase once deemed eligible for enrollment. The run-in phase will be started 7 + 3 days prior to a scheduled visit 2 (vorapaxar dosing day). Subjects will be informed via phone call, a day before, to hold their current home medication of clopidogrel and/or EC ASA the morning of scheduled run-in visit.

If the subject has medical records and safety laboratory test results readily available for review during the screening visit, the run-in phase can be completed at the same time as screening. Instruct subjects to hold home medication of clopidogrel and/or EC ASA the morning of scheduled screening/run-in visit. During this visit, the following procedures will be performed:

- Collection of adverse events.
- Collection of concomitant medications.
- Confirm continue eligibility.
- Administer first dose of study treatment. Document first dose of study treatment as specified below as day 1 of the run-in phase.
 - Group 2: Administer one dose of clopidogrel 75mg orally
 - Group 3: Administer one dose of EC ASA 81mg orally.
 - Group 4: Administer one dose of clopidogrel 75mg and EC ASA 81mg.
- Dispense study drug (EC ASA and/or clopidogrel) for subjects in groups 2, 3, and 4 only.
 - Group 2: 10 tablets of clopidogrel 75mg
 - Group 3: 10 tablets of EC ASA 81mg
 - Group 4: 10 tablets of clopidogrel 75 mg and EC ASA 81mg
- Provide patient education (for EC ASA and/or clopidogrel).
- Provide subject instructions.

To continue on their prescribed antiplatelet regimen, clopidogrel and/or EC ASA; however, the medications will be provided to the subjects by the study site with the following instructions::

 - Group 2 subjects: Take clopidogrel 75mg orally once a day starting the next day, preferably in the morning.
 - Group 3 subjects: Take EC ASA 81mg orally once a day starting the next day, preferably in the morning.
 - Group 4 subjects: Take clopidogrel 75mg and EC ASA 81mg orally once a day starting the next day, preferably in the morning.
- Provide study drug diary for all subjects. Document first dose of study treatment as day 1 of the run-in phase.

9.2.3 Visit 2

The study coordinator will call the eligible subjects the day before to review protocol instructions and study related activities for Visit 2 and answer any potential questions. Remind the subjects to hold their clopidogrel and/or EC ASA (study medications) and all other medications taken by the subjects regularly. Subjects will be instructed to bring all home medications with them for the appointment to take after the bloodwork and testing. Ask subjects to avoid any high fat foods the morning of the visit. For the Endo-PAT2000 test, the subject needs to abstain from smoking and caffeine 2 hours prior to testing. Subjects also need to hold any vasoactive medications 24 hours prior to the test.

The dosing visit will occur within 3 to 28 days of screening for subjects in group 1. Visit 2 for groups 2, 3, and 4 will occur within 7 + 3 days from the run-in period.

During this visit, the following procedures will be performed:

- Vital signs (blood pressure, heart rate) will be obtained after the subject has been in a sitting position for at least 5 minutes.
- Collection of Study Drug Diary for subjects in groups 2, 3, and 4.
- Study drug accountability will be performed (groups 2, 3, and 4).
- Administer Endo-PAT2000 test.
- Blood and urine samples will be obtained for baseline PD measurements through direct venipuncture. The actual date and clock time of blood/urine sampling will be recorded in the CRF.
- Provide a small snack after blood and urine specimen collection
- If applicable, after lab work collection and endo-PAT2000 test, remind subject to take approved home medications as according to subject's regular schedule. Subjects will receive first dose of vorapaxar 2.08mg orally. After administering first dose of vorapaxar, administer daily dose of study treatment (clopidogrel and/or EC ASA) to subjects as according to assigned group (to prevent a missing dose).
- Subject will return to clinic in 2 hours (+ 60 mins) post vorapaxar dosing time for PD blood draw.
- Collection of adverse events.
- Collection of concomitant medications.
- Dispense study drugs
 - Group 1: A bottle of 37 tablets of vorapaxar 2.08mg
 - Group 2: A bottle of 37 tablets of vorapaxar 2.08mg and 37 tablets of clopidogrel 75mg
 - Group 3: A bottle of 37 tablets of vorapaxar 2.08mg and 37 tablets of EC ASA 81mg.
 - Group 4: A bottle of 37 tablets of vorapaxar 2.08mg, 37 tablets EC ASA 81mg, and 37 tablets of clopidogrel 75mg.
- Provide patient education for vorapaxar
- Remind subject of visit 3 schedule and protocol instructions, which includes avoiding any high fat foods for breakfast, and to hold vorapaxar, clopidogrel and/or EC ASA the morning of visit 3. Instruct subjects to bring all study treatment bottles the next visit.

Subjects will be instructed to contact the research facility if they are experiencing any adverse reactions from the medications.

9.2.4 Visit 3

Subjects will report to research site 24 (+/- 2 hrs) hours after initial vorapaxar dose. Remind subjects in groups 2, 3, and 4 to bring all unused study drugs on this visit. The following procedures will be performed:

- Confirm compliance with dietary restrictions (no high fat foods the morning of visit).
- Collection of adverse events.
- Collection of concomitant medications.
- Obtain laboratory specimens for PD measurements for blood through direct venipuncture
- Obtain urine sample for urine thromboxane. After laboratory specimen collection, while in clinic, instruct subject to take vorapaxar 2.08mg, and assigned study treatment (clopidogrel and/or EC ASA). Document in CRF. Provide patient instructions for study treatment. Instruct subject to continue taking study treatment (clopidogrel and/or EC ASA), as assigned, concurrently with vorapaxar 2.08mg for 30 (+/- 7)days. All other home medications will be continued. See specific instructions below as according to subjects' assigned groups.
 - Group 1: vorapaxar 2.08mg orally once a day starting the next day, preferably in the morning.
 - Group 2: vorapaxar 2.08mg and clopidogrel 75mg orally once a day starting the next day, preferably in the morning.
 - Group 3: vorapaxar 2.08mg and EC ASA 81mg orally once a day starting the next day, preferably in the morning.
 - Group 4: vorapaxar 2.08mg, clopidogrel 75mg, and EC ASA orally once a day starting the next day, preferably in the morning.
- Confirm schedule for visit 4.

Subjects will be instructed to contact research facility if they are experiencing any adverse reactions from the medications. Three days prior to visit 4, the study coordinator will call the subjects and reiterate the importance of not missing the study drug/s dose for the next 3 days until the scheduled clinic visit.

9.2.5 Visit 4

Subjects will report to the research site 30 ± 7 days from initial vorapaxar dose. The day prior to the visit, the study coordinator will call subjects for visit 4 instructions. Remind subjects to avoid any high fat foods, and to hold vorapaxar, EC ASA and/or clopidogrel (for groups 2, 3, and 4) the day of visit 4. For the Endo-PAT2000 test, the subjects need to abstain from smoking and caffeine 2 hours prior to testing. Subjects also need to hold any vasoactive medications 24 hours prior to the test. Remind subject to bring all unused study drugs on this visit and all approved home

medications (to prevent missed concomitant medication doses). The following procedures will be performed during this visit:

- Confirm compliance with dietary restrictions (high fat foods, caffeine).
- Collection of adverse events.
- Collection of unused study medications.
- Review concomitant medications
- Administer Endo-PAT2000 test
- Complete physical exam
- Obtain clinical safety laboratory specimens (comprehensive metabolic panel, complete blood count with platelets and auto differential, hsC-reactive protein) and PD measurements.
- Obtain urine sample for urine analysis and urine thromboxane
- If applicable, after lab work collection and endo-PAT2000 test, remind subject to take study drug(s) and approved home medications as according to subject's schedule.
- Study drug accountability
- Dispense study drug for groups 2, 3, and 4 only.
 - Group 2: 17 tablets of clopidogrel 75mg.
 - Group 3: 17 tablets of EC ASA 81mg.
 - Group 4: 17 tablets of clopidogrel 75 mg and EC ASA 81mg.
- Provide patient instructions
 - Stop taking vorapaxar
 - For groups 2, 3, and 4, continue taking EC ASA and/or Clopidogrel (as according to treatment group)
 - Remind subjects not to take any unapproved medications as per protocol.
- Confirm visit 5 schedule

Three days prior to visit 5, the study coordinator will call the subjects and reiterate the importance of not missing the study drug/s dose for the next 3 days until the scheduled clinic visit.

9.2.6 Visit 5

This visit is scheduled 14 + 3 days of visit 4. The day prior to the visit, the study coordinator will call subjects for visit 5 instructions. Remind subjects not to eat any high fat foods, and to hold EC ASA and/or clopidogrel (for groups 2, 3, and 4) the morning of scheduled visit, and to return any unused study drugs. The following procedures will be performed during this visit:

- Confirm compliance with dietary restrictions (high fat foods)
- Collection of adverse events.
- Collection of concomitant medications.
- Blood/urine sample will be obtained for PD measurements.
- Study drug accountability
- Dispense study drug for groups 2, 3, and 4 only.
 - Group 2: 17 tablets of clopidogrel 75mg.

- Group 3: 17 tablets of EC ASA 81mg.
- Group 4: 17 tablets of clopidogrel 75mg and EC ASA 81mg.
- Confirm visit 6 schedule.

Three days prior to visit 6, the study coordinator will call the subject and reiterate the importance of not missing the study drug/s dose for the next 3 days until the scheduled clinic visit.

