5.2.2 Secondary Analysis

Secondary Analysis endpoint measures are a change in:

- Platelet-fibrin clot generation kinetics by thrombelastography (R, TIP-FCS, TG) at onset and offset vorapaxar treatment compared to pre-dose within and between each treatment group.
- Thrombin generation kinetics (Lag time, peak thrombin production, time to peak thrombin generation, and endogenous thrombin potential) as measured by calibrated automated thrombogram during onset and offset of vorapaxar treatment compared to pre-dose within and between each treatment group.
- 5 μ M ADP-, 15 μ M SFLLRN (TRAP)-and 4 μ g/ml collagen- induced maximal and final aggregation by light transmittance aggregation during onset, maintenance, and offset of vorapaxar treatment compared to pre-dose within and between each treatment group. ADP-and

AA-induced aggregation by TEG-6S Platelet Mapping assay during onset, maintenance, and offset of vorapaxar treatment compared to pre-dose within and between each treatment group.

- Platelet/endothelial and inflammatory biomarkers during onset, maintenance, and offset of vorapaxar treatment compared to pre-dose within and between each treatment group. Reactive hyperemia index (RHI) as assessed using the ENDOPAT system between pre-dose and maintenance therapy within and between the treatment groups.

6 Statistical calculations

Statistical calculations will be carried out using SAS® for Windows, version 9.3 or later (Cary, NC). Within group analyses of change scores (pre and post vorapaxar) will be performed using a paired t-test, or the Wilcoxon signed ranks test if the change scores are sufficiently non-normal. The Shapiro-Wilk test will be used to determine if the change scores are non-normal. A calculated P-value < 0.05 will be considered a significant difference between treatments. A secondary ANCOVA analysis will be performed in each group to examine the factors that explain potential variations in change scores, and model variables will include the baseline test value, age, sex, race, weight, diabetes, antiplatelet response to EC ASA and clopidogrel, smoking, etc.

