9.2.7 Visit 6/ End of Study

The subject will report to research site 14 ± 3 days of visit 5. The day prior to the visit, the study coordinator will call the subjects for visit 6 instructions. Remind the subjects not to ingest any high fat foods and to hold EC ASA and/or clopidogrel (for groups 2, 3, and 4) the morning of scheduled visit, and to return any unused study drug. The following procedures will be performed during this visit:

- Vital signs (blood pressure, heart rate) will be obtained after the subject has been in a sitting position for at least 5 minutes.
- Confirm compliance with dietary restrictions (high fat foods)
- Determine adverse event occurrence and follow-up on previously reported adverse events.
- Collection of concomitant medications.
- Blood/urine samples will be obtained for and PD measurements.
- Return unused study drug for groups 2, 3, and 4.
- Study drug accountability
- If applicable, instruct subject to return to original ASA and/or clopidogrel dose.

At the end of the study, all subjects will return to their original standard of care treatment and for any medical treatment questions, will be instructed to resume follow-up with their primary care team.

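### The pre-dose blood draw is taken under tighter conditions than the onset and offset draws, so the secondary onset and offset changes may mix vorapaxar with visit conditions

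*Combined protocol and SAP*

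**What the plan says.** Section 9.2.3 (Visit 2) sets the conditions for the pre-dose pharmacodynamic (PD) sample. The day-before call says: "Remind the subjects to hold their clopidogrel and/or EC ASA (study medications) and all other medications taken by the subjects regularly". Home medicines are brought to the clinic and taken once blood has been drawn and testing is done. Two further limits apply at that visit: "For the Endo-PAT2000 test, the subject needs to abstain from smoking and caffeine 2 hours prior to testing", and "Subjects also need to hold any vasoactive medications 24 hours prior to the test". The first vorapaxar dose follows, and subjects return about 2 hours later for another PD draw.

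For Visit 3 the stated instructions are to avoid high-fat food at breakfast and "to hold vorapaxar, clopidogrel and/or EC ASA the morning of visit 3". For Visit 5 (section 9.2.6) the call says "Remind subjects not to eat any high fat foods, and to hold EC ASA and/or clopidogrel". For Visit 6 (section 9.2.7) it says "Remind the subjects not to ingest any high fat foods and to hold EC ASA and/or clopidogrel". None of the three mentions other home medicines before the draw, vasoactive drugs, smoking or caffeine. Visit 4 (section 9.2.5) repeats the smoking, caffeine and vasoactive limits and places home medicines after the blood draw and Endo-PAT test.

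Section 5.2.1 defines the primary endpoints as change from pre-dose to maintenance. Section 5.2.2 takes the secondary thrombelastography measures "at onset and offset vorapaxar treatment compared to pre-dose within and between each treatment group", and treats thrombin generation, aggregation and biomarkers in the same way.

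**The concern.** Each onset or offset result is a follow-up value minus the Visit 2 pre-dose value. If the two samples are taken under different conditions, the difference contains whatever those conditions do to the assay as well as what vorapaxar does. A larger sample does not remove a systematic difference of that kind.

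A randomised or untreated comparison group could show how much of the change comes from the conditions. Here all four groups receive vorapaxar (section 3.1.2). The groups are not randomised and are defined by disease and current therapy, so comparing groups cannot be relied on to cancel the effect.

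Onset and offset are named in the first two specific aims (section 1.1), so these secondary results are a substantial part of what the study is meant to show.

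**Working it through.** The plan gives no figure to reproduce on this point. The check is a comparison of the instructions for each PD draw. Sections 9.2.3 to 9.2.7 do not label draws as onset or offset. I read the 2-hour and Visit 3 draws as onset, Visit 4 as maintenance, and Visits 5 and 6 as offset.

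| PD draw | Use | Study clopidogrel/aspirin | Other home medicines | Vasoactive drugs | Smoking, caffeine | Food |
|---|---|---|---|---|---|---|
| Visit 2, pre-dose | reference | held | held until after testing | held 24 h | none for 2 h | no high-fat |
| Visit 2, 2 h (+60 min) post-dose | onset | given before the draw | reminder to take them before the draw | nothing stated | nothing stated | snack given |
| Visit 3, 24 h | onset | held | nothing stated for the draw | nothing stated | nothing stated | no high-fat |
| Visit 4, 30 ± 7 days | maintenance (primary) | held | brought, taken after the draw | held 24 h | none for 2 h | no high-fat |
| Visit 5 | offset | held | nothing stated | nothing stated | nothing stated | no high-fat |
| Visit 6 | offset | held | nothing stated | nothing stated | nothing stated | no high-fat |

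1. **Count.** There are five PD draws after baseline. Visit 4 is close to the reference. The other 5 − 1 = 4 differ from it in their stated conditions, and these are all the onset and offset draws.

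2. **Group 1.** These subjects take no study clopidogrel or aspirin and have stopped vorapaxar after Visit 4. At Visits 5 and 6 their instructions hold no drug at all.

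3. **Exposure is expected.** Current smoking, hypertension and diabetes are qualifying risk factors (sections 2.3.3 and 2.5), so some subjects will smoke or take regular medicines.

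4. **Can it be repaired from the data?** Table 1 reviews concomitant medicines at every visit, and section 9.2.3 records the clock time of sampling. No section asks for the time of the last home medicine, cigarette or caffeine. The ANCOVA variables named in section 6 include smoking, listed beside age, sex and diabetes, but nothing tied to an individual draw. The list is open-ended, but a covariate that was not collected cannot be added later.

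5. **Illustration of consequence.** Inputs: n = 25 per group (section 5.1), a paired t-test at P<0.05 (section 6), two-sided testing (assumed), and no vorapaxar effect. Let d be the mean shift due to visit conditions alone, in SDs of the change score (assumed). The statistic is noncentral t with 25 − 1 = 24 degrees of freedom and noncentrality d × √25 = 5d. The probability of P<0.05 is the mass of that distribution outside ± the 97.5% point of t on 24 degrees of freedom.

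| d (assumed) | 0 | 0.1 | 0.2 | 0.3 | 0.4 | 0.5 |
|---|---|---|---|---|---|---|
| Noncentrality 5d | 0 | 0.5 | 1.0 | 1.5 | 2.0 | 2.5 |
| Probability of P<0.05 | 5% | 8% | 16% | 30% | 48% | 67% |

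The documents give no SD and no effect of these conditions on any assay. The table shows how sensitive the test is to a shift; it does not estimate one.

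**The case against.** The strongest reply is that the smoking, caffeine and vasoactive limits were written for Endo-PAT, which is done only at Visits 2 and 4 (section 4.1). On that view their absence elsewhere is deliberate, and the conditions chosen for PD blood, namely high-fat food and study antiplatelets, are already controlled at Visits 2 to 6. This explains how the difference arose. It does not remove it, because the baseline blood is drawn at the same visit. Nor does it cover the hold on all regular medicines, which is a separate sentence not tied to Endo-PAT.

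Second, subjects may in practice delay their medicines. Section 8.6.1.3.9 tells them to bring approved medicines to clinic, and the Visit 3 instructions are introduced as a list that need not be complete. The line in section 9.2.4 that home medicines continue comes after the draw and looks forward to the treatment period. So it is not certain that subjects arrive at Visits 3, 5 and 6 having taken their morning medicines. That stands, but no text sets a hold at those visits and practice may vary between subjects.

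Third, the study calls itself exploratory (section 5.1) and the endpoints concerned are secondary. That also stands, and it limits the priority of the point.

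A reader might infer that the primary result is compromised too. The documents do not support that. Visit 4 repeats the Endo-PAT limits and puts home medicines after the draw, so a hold is implied even though it is not spelled out as it is for Visit 2.

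**Conclusion.** The difference in stated conditions is clear from the text. It affects the secondary onset and offset changes, including the 2-hour draw; the primary Visit 4 comparison is largely matched. With no vorapaxar-free group and no record of timing, an effect of visit conditions could not be told apart from a drug effect afterwards. Whether any bias is large enough to matter is unknown, as is its direction. The probabilities above rest on assumed shifts, two-sided testing and full groups of 25.

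Three stronger readings are tempting and go beyond the documents:

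- **A common shift in every affected subject, masking onset or mimicking recovery.** Cigarettes, caffeine and various medicines are different exposures, and nothing in the plan gives them one direction.
- **A heavier load in Groups 3 and 4 because of prior MI or PAD.** Groups 1 and 2 qualify through hypertension, diabetes and similar factors and may take such medicines too. No medication data by group are given.
- **Section 6 as an admission that smoking before a draw moves the endpoints.** It lists smoking among subject characteristics, and a habitual smoker is one at every visit.

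The change is worth making because it is cheap and can only be made prospectively.

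**What to change.** 1. Reconcile the pre-visit instructions for the PD draws at Visits 2 to 6 in sections 9.2.3 to 9.2.7, and state for each visit what applies to other home medicines and vasoactive drugs. Which medicine rule applies is for the investigators; Visit 4 should say explicitly what it now only implies.
2. Extend the existing 2-hour smoking and caffeine limit to Visits 3, 5 and 6, and confirm it on the CRF as is already done for diet.
3. At every PD draw, including the 2-hour post-dose draw, record the time of last home medicines, cigarette and caffeine.
4. Prespecify a sensitivity analysis of the onset and offset endpoints using these times, for example by adding to the change-score model whether each condition differed from that subject's pre-dose draw. With 25 per group this will be imprecise.
5. State in the analysis plan that the 2-hour draw follows the snack and home medicines by design. It cannot share one identical rule with the pre-dose draw. Recorded times help there only where subjects differ, so that result needs a caveat.

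The cost is minor inconvenience to subjects, a few CRF fields and revised wording for calls. Day-before calls already exist for Visits 2, 4, 5 and 6, and Visit 3 instructions are given at Visit 2. Any wider hold on medicines would carry a clinical cost that the investigators must weigh; this fix does not ask for one.

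### Run-in can be as short as 4 days in Table 1 but at least 7 elsewhere, and in Groups 2-4 the 2-hour sample alone follows that day's aspirin/clopidogrel dose

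*Combined protocol and SAP*

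**What the plan says.** **Run-in.** The synopsis gives Group 2 at least 7 days of clopidogrel. Section 3.1.1 puts the run-in at 7-10 days. The run-in column of Table 1 (section 9.1) starts it 7 ± 3 days before Visit 2. The note under Table 1 and sections 9.2.1, 9.2.2 and 9.2.3 print 7 + 3. Under 3.1.1, Groups 1 and 2 come from subjects not on antiplatelet therapy, while Groups 3 and 4 are already on their regimen. Section 3.1.2 lets a subject proceed with up to 2 missed run-in doses. The primary endpoint (5.2.1) is change from pre-dose to 3-4 weeks.

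**2-hour sample.** Before Visit 2 (9.2.3) the coordinator is told: "Remind the subjects to hold their clopidogrel and/or EC ASA (study medications) and all other medications taken by the subjects regularly". Baseline blood is drawn and vorapaxar is given. Staff then "administer daily dose of study treatment (clopidogrel and/or EC ASA) to subjects as according to assigned group (to prevent a missing dose"). The same list continues: "Subject will return to clinic in 2 hours (+ 60 mins) post vorapaxar dosing time for PD blood draw". At the other visits the background drugs are withheld until after sampling. For the 24-hour visit, subjects are told "to hold vorapaxar, clopidogrel and/or EC ASA the morning of visit 3". For Visit 4 the instruction is "to hold vorapaxar, EC ASA and/or clopidogrel (for groups 2, 3, and 4) the day of visit 4", and for Visits 5 and 6 it is "to hold EC ASA and/or clopidogrel (for groups 2, 3, and 4) the morning of scheduled visit". Section 5.2.2 makes onset change from pre-dose, within and between groups, a secondary endpoint.

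**The concern.** Group 2 starts clopidogrel at run-in, so the run-in window fixes how much clopidogrel it has had when its baseline is taken. If the window is read differently from one subject to the next, that baseline is not one defined state. Every Group 2 change score, including the primary one, starts from it.

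The 2-hour sample raises a separate question of attribution. Onset effect is a stated aim (1.1), and the study sets out to compare vorapaxar alone with vorapaxar added to aspirin and/or clopidogrel (5.1). In Groups 2-4 two things happen between baseline and 2 hours: the first vorapaxar dose and a further background dose. In Group 1 only the first happens.

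**Working it through.** **Plan's own figure.** 4 groups × 25 = 100, as section 2.2 states. No effect size, SD or power is given, so 25 per group cannot be re-derived. The point does not depend on it.

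**Run-in windows side by side**

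| Place | Window | Minimum | Maximum |
|---|---|---|---|
| Synopsis, Group 2 | ≥ 7 days | 7 | not stated |
| 3.1.1 | 7-10 days | 7 | 10 |
| Table 1, run-in column | 7 ± 3 | 7 − 3 = 4 | 7 + 3 = 10 |
| Table 1 note, 9.2.1, 9.2.2, 9.2.3 | 7 + 3 as printed | 7 | 10 |

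- The printed + could be a lost ±, since 9.2.6 prints 14 + 3 where Table 1 has 14 +/- 3. In that case the last row becomes 4 to 10 and agrees with Table 1, but the conflict with the synopsis and 3.1.1 remains.
- Table 1 also puts Visit 2 of Groups 2-4 at 7-28 days from screening. That rules out a 4-day run-in only when screening and run-in share a visit. Screening on day 0, run-in on day 10 and Visit 2 on day 14 satisfies both Table 1 windows with a 4-day run-in.
- Of the 7 whole-day lengths from 4 to 10, three (4, 5 and 6) fall below 7.
- The day 1 dose is taken in clinic and the Visit 2 dose is held until after baseline, so doses before baseline = run-in days − missed doses. With none missed, 4 days gives 4 and 7 days gives 7. With the two permitted misses, 4 − 2 = 2 and 7 − 2 = 5.

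**Background-drug state at each pharmacodynamic sample, Groups 2-4**

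| Sample | That day's aspirin/clopidogrel |
|---|---|
| Visit 2 baseline | held |
| Visit 2, 2 h (+ 60 min) | taken |
| Visit 3, 24 h | held |
| Visits 4, 5 and 6 | held |

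Five of the six samples are taken with the drugs held. Write the change from pre-dose to 2 hours in Groups 2-4 as V + B, where V is the vorapaxar effect on that background and B is the effect of the extra background dose. No sample follows a background dose without vorapaxar, so B cannot be estimated. Group 1's change is V₁ alone. The contrast with Group 1 is therefore (V − V₁) + B, and the groups are not randomized.

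At 24 hours the last background dose was about a day earlier, as it was at baseline, so the two samples match on time since that dose. They do not match on cumulative doses. By then Group 2 has had one more clopidogrel dose, so B drops out only if clopidogrel's effect is already stable. The match also covers antiplatelet drugs only: the Visit 2 reminder holds all other regular medications, and the Visit 3 reminder does not.

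**Measures exposed.** Section 5.2.2 names 3 thrombelastography + 4 thrombogram + 6 light-transmission (3 agonists × maximal and final) + 2 PlateletMapping = 15 laboratory measures at onset, plus biomarkers. Section 4.3 describes PlateletMapping as the cartridge that monitors response to aspirin and clopidogrel, which is 2 of the 15.

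**Precision if Group 2 subjects are set aside.** The 95% half-width for a mean change, in SD units, is t(0.975, n − 1)/√n. For n = 25 it is 2.064/5 = 0.41. For n = 20 it is 2.093/4.472 = 0.47, and for n = 15 it is 2.145/3.873 = 0.55. The numbers set aside (5 or 10) are assumptions.

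**The case against.** The strongest reply is that no harm is shown. No passage says that one more daily dose moves any assay within 2-3 hours, and Groups 3 and 4 are already on their drugs. The between-group contrasts are non-randomized in any case, and the protocol gives a reason for the Visit 2 order (avoiding a missed dose). All of this stands. It limits the point to attribution and rules out demoting the 2-hour change for every measure. For SFLLRN aggregation, or the thrombogram in platelet-poor plasma, nothing in the text suggests an effect of one extra background dose.

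A reader might infer that onset is undefined, because 5.2.2 gives it no time and Table 1 has no 2-hour column. The documents do not support calling that a defect. Section 4.8 refers the study periods to Figure 1, which is not shown, and onset may be meant to cover both the 2-hour and 24-hour samples.

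A reader might also infer that a 4-day run-in biases the primary result. That would require clopidogrel's effect to be still developing at baseline and to move the primary measures. The documents show neither.

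**Conclusion.** Both parts hold, and the point is minor. The run-in conflict is certain on the text: a minimum of 4 days in one place against 7 in two others, whichever way the + sign is read. It sets Group 2's only planned clopidogrel exposure before baseline. Its effect on the primary endpoint is a possibility, with no size or direction given.

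The sampling order is equally explicit. It leaves the 2-hour change in Groups 2-4, and its comparison with Group 1, inseparable from any effect of that day's background dose. The case is best supported for PlateletMapping ADP and AA. Only secondary onset analyses of a study described as exploratory are touched. The primary maintenance comparison is sampled with background drugs held at both ends, so the sampling order does not affect it. No error rate is attached to either part, because the documents give no shift from which to compute one.

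**What to change.** 1. Reconcile the run-in window across the synopsis, 3.1.1, Table 1 and its note, 9.2.1, 9.2.2 and 9.2.3. No view is taken here on which length is right. Report run-in length for Group 2. If any Group 2 subject falls outside the reconciled window, repeat that group's primary change without them as a sensitivity analysis. If none does, nothing is added.
2. In the analysis plan, with dosing unchanged, base between-group onset comparisons on the existing 24-hour sample, and state the assumption that clopidogrel's effect is stable in Group 2. Keep the 2-hour change for all groups, with a note that in Groups 2-4 it follows the background dose. Treat the 2-hour PlateletMapping ADP and AA changes in those groups as descriptive.

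The cost is a consistency edit and a few sentences of analysis wording, with no new sample or visit. The sensitivity analysis, if triggered, has a somewhat wider interval. The study also gives up a 2-hour ADP/AA onset claim attributable to vorapaxar in Groups 2-4.
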